7.4.1.2. Duration of Maintenance of a $\geq 35\%$ Reduction in Spleen Volume

The duration of $\geq 35\%$ reduction from baseline in spleen volume is defined as the interval between the first spleen volume measurement that is $\geq 35\%$ reduction from baseline and the date of the first measurement that is no longer a $\geq 35\%$ reduction from baseline. If the end date is not observed before the database cutoff, the duration will be censored at the last assessment.

The endpoint will be derived for participants who were randomized and who had at least 1 measurement of $\geq 35\%$ reduction from baseline.

Kaplan-Meier estimates of median duration with 95% CIs will be provided.

The ITT population with spleen volume response before crossover will be used.

A supportive analysis for duration of $\geq 35\%$ reduction from baseline in spleen volume defined as the interval between the first spleen volume measurement that is $\geq 35\%$ reduction from baseline and the date of the first measurement that is no longer a $\geq 35\%$ reduction from baseline that is also a $> 25\%$ increase from nadir will be provided.

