Visit Day (Range)	Screening (Day -35 to Day -8)	Baseline (Day -7 to Day -1)	Day 1	End of Week 2 ± 3 Days	End of Weeks 4, 8, 16, and 20 ± 5 Days	End of Weeks 12 and 24 ± 5 Days	Extension Visits (Every 12 Weeks After Week 24) ± 7 Days	EOT or Early Termination Visit ± 5 Days	Safety Follow-Up (End of Treatment + 30-35 Days)	Survival Follow-Up (Every 12 Weeks ± 2 Weeks)	Notes
Safety assessments											
Record AEs	X	X	X	X	X	X	X	X	X		Body systems with symptoms should be physically examined.
Physical examination	X	X			X	X	X	X	X		Comprehensive physical examination at screening and EOT visits, targeted physical examination at the other visits.
Vital signs, weight, height	X	X			X	X	X	X	X		Height at screening only.
12-lead ECG	X					X*		X			*Week 24 only.
PJP		X		X	X	X	X	X	X		PJP prophylaxis can be started anytime beginning at the baseline visit up to Day 1 and will continue through at least 2-6 months beyond the last dose of study treatment.
Efficacy assessments											
Screening Symptom Form	X										
Spleen palpation	X	X			X	X	X	X	X		
Bone marrow biopsy and aspirate	X*					X*	X*				*Screening or baseline, Week 24, and every 24 weeks thereafter. Screening or baseline not required if biopsy from prior 2 months available (report and samples).

Table 3: Schedule of Activities for Randomized Participants in Group A, in Group B, and After Crossover (Continued)

Visit Day (Range)	Screening (Day -35 to Day -8)	Baseline (Day -7 to Day -1)	Day 1	End of Week 2 ± 3 Days	End of Weeks 4, 8, 16, 20 ± 5 Days	End of Weeks 12 and 24 ± 5 Days	Extension Visits (Every 12 Weeks After Week 24) ± 7 Days	EOT or Early Termination Visit ± 5 Days	Safety Follow-Up (End of Treatment + 30-35 Days)	Survival Follow-Up (Every 12 Weeks ± 2 Weeks)	Notes	
MRI/CT scan of the upper and lower abdomen and pelvis		X				X	X				No MRI/CT scan after Week 144.	
Dispense and/or bring MFSAF v4.0 diary to visit		X	X		X	X						
MFSAF v4.0 diary		Completed every evening from baseline through Week 24										
ECOG performance status	X											
Laboratory assessments*	X	X	X	X	X	X	X	X	X		*Participants will also have laboratory-only visits to collect hematology samples at Week 6, Week 10, Week 30, and every 12 weeks thereafter (except where coincident with study visit); see Table 5 .	
Survival follow-up data collection										X		

Table 4: Schedule of Additional Study Visits for Participants Who Cross Over

Visit Day (Range)	Crossover Visit	4 Weeks Post-Crossover ± 5 Days	Notes
Administrative			

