8.2.3. Imaging

The primary measure of spleen volume will be by MRI (or CT scan in applicable participants). An MRI of the upper and lower abdomen and pelvis will be performed at baseline, Week 12, Week 24, and every 12 weeks thereafter through Week 144. An MRI will be performed with a body coil because the objective is to measure organ volume rather than to find very small lesions. MRIs will be read initially by local radiologists, who will be instructed to not provide a quantitative measure of spleen volume but may provide a qualitative assessment such as enlarged, smaller, larger, and so on. However, should a quantitative result be provided to the investigator, this will not be considered a protocol violation, and the participant will still be evaluable. The local radiologist should assess the scan for quality and send all scans (MRI or CT) to the central imaging laboratory the same day if at all possible. The scans from an individual participant will be read by a central reader. The central imaging laboratory radiologist(s) will be blinded to initial treatment assignment. Spleen and liver volume will be obtained by outlining the circumference of the organ and determining the volume using the validated technique of least squares. The MRI will not determine spleen length below the costal margin because there are no validated approaches for determining this measurement. Procedure-specific training for scanning and image capture will be provided by the vendor and in the Imaging Manual.

An MRI is the preferred method for obtaining spleen volume data. However, CT scans may be performed at the visits where MRI is designated if the participant is not a candidate for MRI (eg, because of the presence of metal clips in the body, because of claustrophobia) or if MRI is not readily available. CT scans will be similarly processed by the same central laboratory as used for MRIs. Procedure-specific training for scanning and image capture will be provided by the vendor. *Note:* The same method (MRI vs CT) must be used for all visits for a given participant unless a new contraindication to the use of MRI occurs (eg, pacemaker insertion).

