8.8.2. Survival Follow-Up

Once a participant has received the last dose of study treatment, has confirmed disease progression, or starts a new MF therapy, the participant moves into the survival follow-up period and should be contacted by telephone, e-mail, or visit at least every 12 weeks (\pm 2 weeks) to assess for subsequent MF treatments and survival status until death, withdrawal of consent, or the end of the study, whichever occurs first.

9. ADVERSE EVENTS: DEFINITIONS AND PROCEDURES FOR RECORDING, EVALUATING, FOLLOW-UP, AND REPORTING

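### The duration-of-spleen-response analysis censors responders who die in response, so its Kaplan-Meier curve and median overstate time alive and in response

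*SAP*

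**What the plan says.** SAP 7.4.1.2 runs the duration from the first scan with at least a 35% reduction to "the date of the first measurement that is no longer a" reduction of that size. No other event ends it. The censoring rule is general: "If the end date is not observed before the database cutoff, the duration will be censored at the last assessment". Death, permanent treatment stop and new MF therapy are not mentioned, so they fall under that rule. On the estimator: "Kaplan-Meier estimates of median duration with 95% CIs will be provided". On the analysis set: "The ITT population with spleen volume response before crossover will be used". Protocol Table 17 likewise lists Kaplan-Meier estimation only.

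The one supportive analysis adds a rise of more than 25% from nadir to the definition of loss. That is a stricter event, so durations can only lengthen.

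Scans take place at baseline, Week 12, Week 24 and "every 12 weeks thereafter through Week 144" (Protocol 8.2.3). In Protocol Table 3 the row "MRI/CT scan of the upper and lower abdomen and pelvis" is blank at the end-of-treatment, safety follow-up and survival follow-up columns. Protocol 8.7 triggers the end-of-treatment visit when both drugs are permanently stopped, and lets it replace a coinciding scheduled visit. Protocol 8.8.2 moves the participant to survival follow-up "Once a participant has received the last dose of study treatment, has confirmed disease progression, or starts a new MF therapy". From then on only later MF treatment and survival status are collected.

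**The concern.** A participant who has died can no longer show a loss scan. Censoring at the last assessment lets the Kaplan-Meier estimator treat that person as someone who would have gone on in response like those still observed. The result is time to measured loss in a setting without death. A reader of a table titled duration of maintenance will take it as how long responders kept the benefit.

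The matching objective in Protocol Table 7 and SAP Table 1 is to compare this duration between arms. If death rates differ by arm, the two curves are overstated by different amounts. The plan is also not uniform on stopping: SAP 7.3.1 counts treatment discontinuation before Week 24 as nonresponse for the primary endpoint, whereas after a response the same event is a censoring.

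**Working it through.** **Inputs from the documents (Protocol 10.1, SAP 3.3).** Control median survival 5.3 years; hazard ratio 0.54; 85 deaths; 80% power; 1.5 years of accrual; analysis at about 3 years. Neither document gives a rate of response loss or of treatment stop, so those below are assumptions.

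**Step 1. Reproduce the plan's survival figures.** Events needed, by Schoenfeld's formula: 4 × (1.960 + 0.842)² / (ln 0.54)² = 83, against 85 stated. Power at 85 deaths is 0.81, against 0.80 stated. With exponential survival, 220 per arm and uniform accrual, expected deaths are 84.6 at 2.9 years and 88.1 at 3.0 years. The plan's death rates are coherent.

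**Step 2. Death hazards.** Control: ln 2 / 5.3 = 0.131 per year. Parsaclisib arm under the plan's alternative: 0.54 × 0.131 = 0.071 per year.

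**Step 3. Factor between the SAP curve and the share alive and in response.** If death and loss are independent, share(t) = SAP curve(t) × exp(−hazard × t). With 52.18 weeks per year, 48 weeks is 0.920 years and 96 weeks is 1.840 years.

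| | 48 weeks | 96 weeks |
|---|---|---|
| Control hazard 0.131 | 0.89 | 0.79 |
| Hazard ratio 0.54 (0.071) | 0.94 | 0.88 |

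The factor does not depend on the loss rate.

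**Step 4. Illustration with assumed loss rates.** At a loss rate of 0.15 per year the SAP curve at 2 years is exp(−0.30) = 74%. The share alive and in response is exp(−2 × (0.15 + 0.131)) = 57% at the control hazard and exp(−2 × (0.15 + 0.071)) = 64% at hazard ratio 0.54.

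A simulation (200,000 responders per scenario, scans every 12 weeks, 120 weeks of follow-up, control death hazard, no stopping) gives:

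| Assumed median time to loss | SAP rule, 96 weeks | Death as event, 96 weeks | Median, SAP rule | Median, death as event |
|---|---|---|---|---|
| 72 weeks | 0.40 | 0.31 | 72 weeks | 60 weeks |
| 120 weeks | 0.57 | 0.45 | 120 weeks | 84 weeks |
| 200 weeks | 0.72 | 0.56 | not reached | 120 weeks |

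With neither deaths nor stopping, all versions agree (0.574 at 96 weeks for a 120-week median).

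**Step 5. Difference between arms.** Let both arms lose response at the same rate (median 120 weeks). Both SAP curves stand at 0.57 at 96 weeks. The shares alive and in response are 0.57 × 0.79 = 0.45 and 0.57 × 0.88 = 0.50. The SAP analysis would show no difference.

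**Step 6. Stopping both drugs.** Take a 120-week median to loss and 20% per year stopping. If the loss rate is unchanged after stopping, the true share alive and in response at 96 weeks is 0.45, equal to the death-as-event curve. Censoring at the stop then adds no bias. If response is lost three times faster off treatment, the true share is 0.39. If stopping is defined as the end of maintenance, the figure is 0.31.

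**The case against.** Time to measured loss is a legitimate quantity, and the event and censoring rules are explicit. Choosing it over a composite is a choice of estimand, not an arithmetical error. The endpoint is secondary, has no planned test and lies outside the alpha-controlled sequence. Deaths and reasons for discontinuation are already to be reported by arm. This stands as far as severity goes. But the SAP does not say that the curve sets death aside, and the planned tables do not show how follow-up ended among responders.

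The size is also uncertain. The 5.3-year median applies to the whole control arm, and responders may die less often. That stands too.

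Three stronger readings are tempting, and the documents do not support them.

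- *A reader might infer that the analysis flatters parsaclisib because toxicity leads to more stops.* No stop rates are given, and Step 6 shows that a stop biases the curve only under an added condition. Scanning ends when both drugs stop. Protocol 6.7.6 speaks of stopping the study drug, while 7.1.1 lists unacceptable toxicity as a reason to stop both; the two need reconciling before anyone can say how many toxicity stops end imaging. Exits for at least 25% spleen growth over baseline already contain a loss scan. Under the plan's own hazard ratio, death inflates the placebo curve more.
- *A reader might infer that the medians would be years apart.* Scans end at Week 144, so a response first seen at Week 12 can be followed for at most 132 weeks, about 2.5 years. Medians beyond that are extrapolation.
- *A reader might measure the overstatement as one minus Kaplan-Meier against the cumulative incidence of loss.* That comparison runs the other way: Kaplan-Meier shows more loss than the cumulative incidence.

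**Conclusion.** The concern holds for death. The direction is certain: turning a censored time into an event at that time can only lower a Kaplan-Meier curve or leave it unchanged. Under independence the SAP curve must be multiplied by about 0.79 at 96 weeks at the plan's control death rate, or about 0.88 with hazard ratio 0.54, to give the share alive and in response. For a curve at 0.57 that is an overstatement of about 12 or 7 percentage points. These sizes rest on whole-arm death rates, constant hazards and, for the curve level, an assumed loss rate. The true size cannot be derived from the documents.

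For permanent stop of both drugs the concern is conditional: it needs faster loss off treatment, or a definition of maintenance that ends at the stop. The consequence is for the description and comparison of durability, not for type I error. It is a worthwhile improvement of modest priority.

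**What to change.** In SAP 7.4.1.2, and in Tables 2.2.1.2 and 2.2.1.3:

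1. State whether the target is time to measured loss or time alive and in response.
2. Add a Kaplan-Meier duration that counts death as an end of maintenance. State how a death after scanning has stopped is handled, since response status is then unknown.
3. Add a sensitivity version that also ends maintenance at permanent discontinuation of both drugs or at new MF therapy.
4. Tabulate by arm how each responder's follow-up ended: loss scan, death, stop or new therapy, crossover, or data cutoff.

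If a cumulative incidence of loss is shown, present it only beside the cumulative incidence of the competing events. Alone it favours the arm with more of them: with loss at 0.15 per year in both arms, the 2-year cumulative incidence of loss falls from 23.6% to 19.3% as the competing hazard rises from 0.10 to 0.33 per year. The formula is 0.15/(0.15 + c) × (1 − exp(−2 × (0.15 + c))), where c is the competing hazard.

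Cost: SAP wording and a little more analysis from data already collected, with no new visits, sample size or alpha. The reported duration will be shorter.

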7.4.2. MFSAF Total Symptom Score v4.0

The MFSAF v4.0 is composed of 7 individual symptom scores (fatigue, night sweats, itchiness, abdominal discomfort, pain under left ribs, early satiety, bone pain), each collected daily with a 0- to 10-point scale.

The daily MFSAF TSS is the sum of the 7 individual symptom scores collected on the same day. The MFSAF TSS will be missing if there are any missing individual scores. Observations with missing dates will be excluded from the analysis.

The baseline total score is defined as the average of daily total scores from the last 7 days before the first dose of parsaclisib, placebo, or ruxolitinib; the baseline total score will be missing if there are ≥ 4 missing out of the 7 daily total scores.

The Week 12 total score will be the average of daily total scores from the first 7 consecutive days starting Day 78; the Week 12 total score will be missing if there are ≥ 4 missing out of the 7 daily total scores.

The Week 24 total score will be the average of daily total scores from the 7 consecutive days before the Week 24 visit; the Week 24 total score will be missing if there are ≥ 4 missing out of the 7 daily total scores.

The percentage change from baseline to Week 12/Week 24 will be calculated using the following formula:

$$\% \text{ change} = 100 \times [\text{Week 12/Week 24 MFSAF TSS} - \text{baseline MFSAF TSS}] / \text{baseline MFSAF TSS}.$$

7.4.2.1. Windowing of MFSAF v4.0 Total Symptom Score

7.4.2.1.1. MFSAF v4.0 Total Symptom Score for Non – Time-to-Event Endpoints

The MFSAF v4.0 TSS for baseline, Week 12, and Week 24 will be determined by averaging the daily MFSAF v4.0 TSS for the days between the start and end of windows as described in [Table 2](#). By-question summaries for the 7 individual symptom scores that compose the MFSAF TSS at baseline, Week 12, and Week 24 will use the same windowing algorithm as used for the daily TSS.

The TSS and the 7 individual scores at Weeks 4, 8, 16, and 20 will be derived in a similar fashion using the first nonmissing daily TSS available between

Day $(7 \times \text{week}) - 6$

and

Day $(7 \times \text{week})$

as the start of the window.

Table 2: Window for Deriving MFSAF v4.0 Total Symptom Score for Baseline, Week 12, and Week 24

Period	Start of Window	End of Window	Missing
Baseline	7 days on or before end of window	Last day that a daily TSS was collected between Day -7 and Day -1 (inclusive)	4 or more missing of the 7 daily TSSs in the window
Week 12	First day a daily TSS was collected between Day 78 and Day 84 (inclusive)	7 days on or after start of window	4 or more missing of the 7 daily TSSs in the window
Week 24	7 days on or before end of window	The day before Week 24 visit	4 or more missing of the 7 daily TSSs in the window

7.4.2.1.2. MFSAF v4.0 Total Symptom Score for Time-to-Event Endpoints

The MFSAF v4.0 TSS for baseline will be derived as the same way in Section [7.4.2.1.1](#). The daily postbaseline TSS will be calculated from Day 7 to the day before the Week 24 visit. The Day X TSS is the average TSS between Day $(X - 6)$ and Day X. For example, the TSS on Day 7 is the average of the TSS from Day 1 to Day 7. The missing individual score and the missing daily TSS will follow the rule defined in Section [7.4.2](#).

7.4.2.2. Proportion of Participants With a $\geq 50\%$ Reduction in MFSAF v4.0 Total Symptom Score

The difference between parsaclisib plus ruxolitinib and placebo plus ruxolitinib in the proportion of participants who have a $\geq 50\%$ reduction in TSS from baseline to Week 24 evaluated by MFSAF v4.0 will be assessed using CMH test stratified by baseline (or screening, if applicable) platelet count and DIPSS category at randomization for the ITT population as primary analysis and PP population as sensitivity analysis. In the case that there is an insufficient number of participants enrolled in any DIPSS level within a platelet category, the collapsing rule specified in Section 7.3.1 will be applied. Missing values will not be imputed.

The percentage change from baseline to Week 24 will be calculated using the following formula:

$$\% \text{ change} = 100 \times (\text{Week 24 total score} - \text{baseline total score}) / \text{baseline total score}.$$

A participant will be considered as having achieved $\geq 50\%$ reduction of the TSS from baseline to Week 24 if the participant had both baseline and Week 24 TSS, the participant did not make an early crossover to receive parsaclisib plus ruxolitinib before the Week 24 visit, and the percentage change from baseline was not missing and was $\leq -50\%$.

A participant who has a missing Week 24 TSS, discontinued treatment before Week 24, is unblinded prior to Week 24 for early crossover to parsaclisib plus ruxolitinib, or has a baseline value of 0 will be considered as having not achieved the $\geq 50\%$ reduction.

A participant who has a missing baseline assessment will be considered as nonevaluable.

At the time of interim analysis, a participant who is still on treatment, but has no timepoint assessment for TSS, will also be considered as nonevaluable.

7.4.2.3. Mean Change and Percentage Change in MFSAF v4.0 Total Symptom Score

The mean change and percentage change from baseline to Week X will be calculated using the following formula:

$$\% \text{ change} = 100 \times (\text{Week X total score} - \text{baseline total score}) / \text{baseline total score}.$$

The mean change and percentage change in TSS, the 7 individual scores, the total score of the 3 spleen-related symptom, including abdominal discomfort, pain under left ribs, and early satiety from baseline to Week X, will be summarized descriptively by treatment group and every 4 weeks using the ITT population. Missing values will not be imputed.

A plot of percentage change from baseline in MFSAF TSS at each visit will be provided.

7.4.2.4. Time to the First $\geq 50\%$ Reduction in Myelofibrosis Symptom Assessment Form v4.0 Total Symptom Score

The time to the first $\geq 50\%$ reduction in TSS is defined as the time from randomization to the first time participants had $\geq 50\%$ reduction in TSS. The daily TSS will be calculated according to the algorithm defined in Section 7.4.2.1.2. Participants with valid calculated baseline TSS and at least 1 postbaseline TSS who do not have $\geq 50\%$ reduction in TSS at the time of analysis will be censored at the time of the last valid calculated TSS. If the participants have no valid calculated baseline or postbaseline TSS, they will be censored at the date of randomization.

The stratified log-rank test will be used to compare time to the first $\geq 50\%$ reduction in TSS between 2 treatment groups in the ITT population at a 1-sided 2.5% significance level, stratified for baseline (or screening, if applicable) platelet count and DIPSS category. The strata identified in the randomization process will be used for the analysis.

Kaplan-Meier curves for time to the first $\geq 50\%$ reduction in TSS will be presented by treatment groups. The KM estimate of median time to the first $\geq 50\%$ reduction in TSS will be presented with its 95% CI. The 95% CI will be calculated using the generalization of method of Brookmeyer and Crowley (1982) with log-log transformation (Klein and Moeschberger 1997).

